6 DATA MANAGEMENT

6.1 Source Documentation Requirements

Source documents and access to source data and documentation will be maintained according to Good Clinical Practice (GCP) guidelines. The investigators will maintain and securely store complete, accurate, and current study records throughout the study. In accordance with U.S. regulations, the investigators will retain all study records on-site for at least two years after study closure. Applicable records include survey instruments and recordings, data collected in the OARS platform, and notations of all contacts with participants.

6.2 Quality Control and Quality Assurance

Study investigators will maintain ongoing quality control procedures which include standard source documentation practices and accurate informed consent procedures, among others. They will also be responsible for providing proper training to study staff and documentation of this training.

6.3 Data Analysis

Data will be collected pre and post integration of the OARS platform within the EHRs of six clinics. The primary analyses will focus on examining outcomes from the index visit versus 6 months post implementation of OARS. The analyses will assess the effect of OARS on study outcomes. The primary predictor of interest will be the OARS intervention compared to TAU. Descriptive and repeated measure analyses will be conducted to test the hypotheses that OARS condition will result in increased number of patients treated with MAT, increased retention, and increased opioid abstinence compared to TAU. We will consider several clinic-level factors potentially associated with the study outcome, including clinic size, duration of the clinics' MAT program, and ancillary clinic services.

The secondary analysis will use data from patients treated after OARS implementation. A logistic regression model will be employed to estimate effect of provider and patient engagement with the OARS platform (number of days of OARS engagement, number of interactive features used) on patient opioid abstinence (opioid-negative urine toxicology). We will adjust for patient-level covariates including demographic variables (age, gender, race/ethnicity, level of education), other substance use, severity of opioid use, and medical comorbidities.

Exploratory analyses will facilitate estimation of ROI for OARS. We will use estimates from the primary analysis of the relative counts of services provided to patients before and after OARS as a key parameter. Additional service utilization will be added in order to estimate a distribution of service utilization beyond the six month study period and for a hypothetical, broader group of patients. We will vary the parameters for the distribution of service utilization in order to show sensitivity of subsequent ROI estimates to key assumptions. The service utilization estimates will be applied to financing scenarios in order to calculate alternative ROI estimates. These will include a traditional fee-for-service model, essentially multiplying utilization by their associated reimbursement amounts (e.g., outpatient counseling visit, medication management visit) under different payer scenarios, including Medicaid. We will also estimate ROI under value-based payment (VBP) models with quality incentives, e.g., CMS' Merit-based Incentive Payment System (MIPS). Under these types of models, eligible providers can receive bonus revenue for achieving quality and other goals. Such criteria can include the use of telehealth, provision of enhanced services, and treatment retention. Because many of these models are still being developed and modified, we will also use sensitivity analyses to characterize uncertainty in the future payer landscape. In addition to the revenue component of ROI, we will also account for changes in costs to payers including additional labor effort in service delivery with OARS and direct software costs.

All analysis will be conducted using SAS version 9.4 (Cary, NC).

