3 STUDY DESIGN

3.1 Description of Study Design

This study tests whether MAT in the primary care setting delivered via the OARS platform can result in improved clinic-level outcomes compared to TAU using a stepped-wedge effectiveness trial design (see Figure 1). This design facilitates data collection on patient outcomes prior to implementation of OARS, data that is individual to each clinic and that will serve as baseline values. In turn, baseline data collected under TAU will be compared to corresponding data collected through OARS for the purpose of assessing whether OARS use results in improved outcomes. This study design necessitates data collection only through EHR data review and abstraction; no information is required directly from patients for the purpose of this study.

Figure 1. Study Design

	Months 1-4	Months 5-8	Months 9-12	Months 13-16	Months 17-20
Clinic					
1	TAU		OARS		
2					
3	TAU		OARS		
4					
5	TAU			OARS	
6					

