3.2 Summary of Study Endpoints

The following primary outcomes will be assessed under TAU and OARS conditions:

- 1) Number of patients PCPs can treat using MAT in primary care settings;
- 2) Retention in treatment (number of patient visits kept with PCPs, length of stay in treatment);
- 3) Proportion of opioid-free urine tests.

The secondary outcome of opioid abstinence, defined as opioid-negative urine toxicology, will be assessed on a patient level as patients are treated for OUD under the OARS condition.

Exploratory outcomes will include additional elements from several administrative sources, namely meta-data from OARS software and additional detail on records of service delivery from the providers'

electronic health records, claims database, and OARS. OARS meta-data will primarily be time stamps around key service delivery or key OARS activities to account for differences in time spent during traditional clinical service delivery and possible additional wrap-around activities. Service delivery measures will include the number of units of different services provided to each patient over time.

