5 STUDY PROCEDURES

The OARS platform is owned and maintained by Q2i. For the purpose of conducting this study, Q2i is partnering with researchers from the UCLA Departments of Family Medicine and Psychiatry and Biobehavioral Sciences to execute the research at each of the six participating clinics.

The research team, composed of study staff at both Q2i and UCLA, will determine the order of implementation of the OARS platform by clinic. Study staff will then notify each clinic of the start date of the OARS platform implementation for their clinic. Following start date assignment, the baseline phase of the study will commence in which patients will receive standard treatment for OUD provided by each clinic (TAU).

Data collected will include both patient-level indicators from each clinic's EHR (see data collection tool) and provider-level indicators obtained from interviews with PCPs. Baseline data will provide an assessment of TAU for up to a period of four (clinics one and two), eight (clinics three and four), and 12 (clinics five and six) months prior to implementation of the OARS platform. Study staff will provide each clinic with relevant data collection specifications and each clinic's IT staff will be responsible for submitting requested data elements from the clinic's EHR to Q2i through secure file transfer. Up to two PCPs from each clinic will be interviewed (see semi-structured interview guides) during TAU, at one month after OARS implementation, and at the end of the OARS period. Eligible PCPs will receive a recruitment letter that outlines the study activities with a request for interested providers to contact study staff at UCLA.

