Concurrently with baseline data collection, study staff will also work with clinics to initiate the OARS platform according to the determined start date. Clinics will begin using the OARS platform with all MAT patients seen at that time. Therefore, patients receiving TAU when the OARS platform is implemented will shift care to using OARS. Patient care and treatment of OUD will then commence under the OARS condition for a period of eight months for each clinic. To compare outcomes under the OARS condition to those that occurred under TAU, comparable data will be directly collected through the OARS platform. Additionally, patient-level data collected during the OARS condition will be used to assess to what extent different levels of provider and patient engagement with OARS relate to opioid abstinence among patients. Data elements of interest (patient demographics, medications, and billing information) that are not transmitted through OARS will be obtained from each clinic's EHR and delivered directly to Q2i through secure file transfer.

All patient-level data will be collected via the EHR and transmitted to Q2i study staff via a secure file transfer system. Patients' medical record identifier will be included in each of the data transmissions to link data across TAU and OARS conditions. No one outside of the Q2i engineer will have access to patient identifiers across both conditions. Patients will not be required to submit any data for the purpose of this research. Providers will be interviewed by UCLA study staff. Interviews will be transcribed and the transcripts will be de-identified prior to sharing with Q2i staff.

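### The primary contrast is index visit versus 6 months after OARS, with no calendar-time term specified and the index visit undefined; used without time adjustment it counts background change as OARS effect

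*Combined protocol and SAP*

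**What the plan says.** Section 3.1 describes MAT delivered through OARS as "compared to TAU using a stepped-wedge effectiveness trial design (see Figure 1"). Section 5 gives the layout. Baseline is "TAU for up to a period of four (clinics one and two), eight (clinics three and four), and 12 (clinics five and six) months" before implementation. At rollout, "patients receiving TAU when the OARS platform is implemented will shift care to using OARS". Then: "Patient care and treatment of OUD will then commence under the OARS condition for a period of eight months for each clinic".

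Section 6.3 is the only analysis section. Its statement of the primary contrast is: "The primary analyses will focus on examining outcomes from the index visit versus 6 months post implementation of OARS". It makes OARS versus TAU the main predictor and names descriptive and repeated-measures analyses without giving a model. On covariates it adds: "We will consider several clinic-level factors potentially associated with the study outcome, including clinic size", followed by how long the clinic's MAT program has run and its ancillary services. Calendar time, period and step are not mentioned there or elsewhere. The term *index visit* occurs once and is not defined.

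The three primary outcomes in Section 3.2 differ in kind. The first is a clinic-level count, "Number of patients PCPs can treat using MAT in primary care settings". The second is retention (visits kept and length of stay). The third is the proportion of opioid-free urine tests.

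**The concern.** A stepped wedge can separate an intervention from calendar time only through the staggered start, which lets clinics already on OARS be compared with clinics still on TAU in the same months. The contrast in Section 6.3 is a before-after comparison within clinic. Without a time term, it cannot tell an OARS effect from anything else that changed over up to 20 months. The TAU data from months 5-12 then lose their role as concurrent controls. An effect could be created or hidden, depending on the direction of drift.

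The contrast also fits some outcomes poorly. A number of patients treated by a clinic has no index visit. Length of stay is not a two-point measurement when patients in treatment at rollout cross from TAU to OARS.

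**Working it through.** **The plan's own figure.** Section 4.1 says at least 200 patients are needed for power. This cannot be reproduced, because no alpha, power, effect size, base rate, intraclass correlation or test is given. Six clinics at the 35-patient minimum in Section 4.2 make 6 × 35 = 210, which shows only that the eligibility floor exceeds 200.

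**Layout (Section 5).** OARS starts after month 4, 8 or 12, two clinics each, and runs 8 months. In five 4-month periods this gives 24 clinic-period cells:

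| Months | 1-4 | 5-8 | 9-12 | 13-16 | 17-20 |
|---|---|---|---|---|---|
| Clinics on TAU | 6 | 4 | 2 | 0 | 0 |
| Clinics on OARS | 0 | 2 | 4 | 4 | 2 |

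The sixth OARS month is study month 10, 14 or 18. Only month 10 has concurrent TAU data (clinics 5-6).

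**Apparent effect of the stated contrast.** With no OARS effect and a common drift of b points per month, the apparent effect is b × mean gap in months. The values of b are assumptions; the gaps follow from the layout.

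| Reading of index visit | Gaps | Mean | b = ±0.5 | b = ±1 |
|---|---|---|---|---|
| Last TAU month | 6, 6, 6 | 6 | ±3 | ±6 |
| All TAU months vs OARS months 1-6 | 5, 7, 9 | 7 | ±3.5 | ±7 |
| Study month 1 | 9, 13, 17 | 13 | ±6.5 | ±13 |

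The undefined term alone changes the result by a factor of 13/6 ≈ 2.2.

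**With period effects.** Least squares on the 24 cell means, with clinic effects, period effects and an OARS indicator, returns 0 for any common drift. The variance factor for the OARS effect is 0.706 on 24 − 11 = 13 df. A clinic-only model has 0.174 on 24 − 7 = 17 df. The ratio is 0.706/0.174 ≈ 4.

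**What that costs.** Assume 35 independent tests per cell and 50% negative.
- SE: √(0.706 × 0.25/35) = 7.1 points, versus √(0.174 × 0.25/35) = 3.5 points.
- 80%-power detectable difference, using t quantiles (2.16 + 0.87 = 3.03 on 13 df; 2.11 + 0.86 = 2.97 on 17 df): 3.03 × 7.1 = 21.5, versus 2.97 × 3.5 = 10.4 points.
- Detectable count ratio at 35 patients per cell (independent Poisson): exp(3.03 × √(0.706/35)) = 1.54, versus exp(2.97 × √(0.174/35)) = 1.23.

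**Limit of the adjustment.** It assumes one calendar trend for all clinics. If slopes are 0, 0.5 and 1 point per month from the earliest to the latest pair, it leaves −2.1 points; in the reverse order, +2.1. Clinic-specific linear trends remove this, at a variance factor of 0.833 on 8 df (0.833/0.706 = 1.18, or 18% more).

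**Length of stay needs time since treatment start as well.** Section 1.1 says most patients who enter MAT stop early, so the discontinuation hazard plausibly falls with time in treatment. Illustrative assumptions: 35 patients and 2 arrivals per month per clinic; monthly hazards of 20%, 10% and 3% in months 0-2, 3-5 and 6 onward; and 50%, 25% and 0% newly started patients in the initial caseload from the earliest to the latest pair. With no OARS effect and no drift, a model with clinic and period only gives a hazard ratio of 0.72, or 1.40 with the shares reversed. Adding time since treatment start gives 1.00 in both.

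**The case against.** The strongest reply is that the plan is underspecified rather than wrong. It names a stepped wedge, makes OARS versus TAU the predictor and promises repeated-measures analyses, any of which could carry a period term. This stands. A reader might infer that the sponsor has chosen an unadjusted before-after analysis, but the documents do not say so and the bias is conditional. What remains is that the one sentence defining the primary contrast permits both a biased and an unbiased analysis.

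A second reply is that duration of the clinic's MAT program would absorb time. It is only to be considered, as a clinic-level factor. Recorded once per clinic, it removes no drift. Updated over time alongside clinic effects, it acts as linear time; a 5-point common step at month 13 or 17 would still leave +0.75 or −0.71 points. The text does not say which is meant.

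Third, every drift above is assumed, and the mildest case is only 3 points. That is also fair; the documents give neither the size nor the direction of any trend.

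Two further inferences go too far. A clinic-effects-only model on all periods would turn 1 point per month into 8.4 points, but the protocol never proposes that model, so this is not the plan's bias. Nor are the TAU data of months 5-12 necessarily unused: if all TAU months form the baseline they enter for clinics 3-6, and only their role as concurrent controls is lost.

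**Conclusion.** The concern holds in conditional form. The primary contrast is stated as before versus after, no time adjustment is specified, and one end of the contrast is undefined. Used without a time term, it converts each 1 point per month of common drift into 6 to 13 points of apparent effect, depending on the reading of index visit. These multipliers rest only on the layout in Section 5 and a linear drift common to all clinics; the drift itself is assumed.

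The documents do not support saying that time will be omitted or that a trend exists. Nor do they show that the rollout order is non-random: Section 5 says only that the research team "will determine the order of implementation of the OARS platform by clinic". The defect lies in the specification of the primary analysis and should be corrected before outcomes are compared.

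**What to change.** Replace the sentence in Section 6.3 with a primary model on all TAU and OARS clinic-periods: clinic effects, categorical calendar-period effects and a time-varying OARS indicator. Use inference suited to six clinics, for example clinic-period means with t on the residual df. By outcome:

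- **Patients treated:** a count per clinic-period.
- **Visits kept and urine tests:** the same structure, accounting for repeated measures within patient.
- **Length of stay:** time to discontinuation, with OARS as a time-varying exposure, adjusted for calendar period and time since treatment start. This assumes treatment start and stop dates are available.

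Delete *index visit*, or define it and keep it for secondary description. State the common-trend assumption, and add clinic-specific linear trends as a sensitivity analysis only. State how the rollout order is assigned, and whether MAT program duration is recorded once or updated; it does not replace period effects.

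Apart from those dates, the model uses data already planned in Section 5. The cost is the precision loss worked out above, under assumptions of independent cells and 35 per cell; following the same patients across periods would change those figures. Section 4.1 should therefore re-justify the 200-patient statement under this model, or restate what the trial can detect.

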4 STUDY POPULATION

4.1 Selection of the Study Population

The study population will consist of six primary care clinics who prescribe MAT (Suboxone or buprenorphine) to patients with OUD. Across all six clinics, there is a minimum of 200 patients needed to provide statistical power to assess primary and secondary objectives.

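### Section 6.3 tests the three primary hypotheses without making clinic the unit of inference or fixing a test valid for six clinics; common forms of the named analysis would reject a true null far more than 5% of the time

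*Combined protocol and SAP*

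**What the plan says.** Section 4.1 fixes the number of clusters: "The study population will consist of six primary care clinics who prescribe MAT (Suboxone or buprenorphine) to patients with OUD". Section 3.1 describes the trial as "using a stepped-wedge effectiveness trial design (see Figure 1"). Section 5 gives usual-treatment phases of up to "four (clinics one and two), eight (clinics three and four), and 12 (clinics five and six) months prior to implementation", followed by care "under the OARS condition for a period of eight months for each clinic". It also says that at go-live a clinic uses OARS for all its MAT patients and that patients already in care move across. Section 2.1 calls the primary outcomes clinic-level.

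The primary analysis in section 6.3 consists of three elements:

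- the contrast: "The primary analyses will focus on examining outcomes from the index visit versus 6 months post implementation of OARS";
- the method: "Descriptive and repeated measure analyses will be conducted to test the hypotheses that OARS condition will result in increased number of patients", and likewise for retention and abstinence;
- the software: "All analysis will be conducted using SAS version 9.4".

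Some clinic characteristics are to be considered as covariates. No section names the clustering unit, a period effect, a covariance structure, a variance estimator, degrees of freedom, a small-sample correction, a significance level or sidedness.

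**The concern.** Exposure changes by clinic, so patients and months within a clinic do not supply independent information on the OARS effect. Two familiar forms of repeated-measures analysis are vulnerable here:

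- **Generalised estimating equations (GEE) with an uncorrected sandwich variance and a normal reference.** This relies on many clusters. With six, the variance is biased downwards and the reference distribution is too narrow.
- **A random clinic intercept (exchangeable) model with residual degrees of freedom.** This treats all months within a clinic as equally correlated. MAT caseload is a running stock, so adjacent months are likely to be more alike than distant ones.

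A third form, treating patients as independent and leaving clinic out, is also not excluded. At stake is the error rate of the answer on all three primary outcomes, and the length of their intervals. Section 6.3 also carries the primary estimates of service counts into the return-on-investment work.

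**Working it through.** **No figure to reproduce.** The only design figure is the minimum of 200 patients in section 4.1. No alpha, power, effect size or intraclass correlation (ICC) accompanies it. The check is therefore of the false-positive rate, by simulation with no OARS effect.

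**Layout, from sections 4.1 and 5.**
- Usual-treatment clinic-months: 2×4 + 2×8 + 2×12 = 48.
- OARS clinic-months: 6×8 = 48, so 96 in all, with clinics observed for 12, 16 or 20 months.
- In 4-month periods: 2×1 + 2×2 + 2×3 = 12 usual-treatment cells and 6×2 = 12 OARS cells.

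**Assumptions, not in the documents.** Two-sided 5% level; normal outcomes; and two models for the data.
- Model A: clinic-month value = clinic effect + AR(1) error, monthly autocorrelation ρ = 0, 0.5, 0.8 or 0.9. Up to 3,000 data sets per setting.
- Model B: 35 patients per clinic per 4-month period (35 being the clinic minimum in section 4.2), ICC 0.05 or 0.10, cluster autocorrelation (CAC) 1.0, 0.8 or 0.5. 1,500 data sets per setting; simulation standard error √(0.05×0.95/1500) = 0.6 points at 5% and √(0.2×0.8/1500) = 1.0 point at 20%.

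**A check without simulation.** Suppose a statistic really follows a t distribution on 4 or 5 degrees of freedom but is compared with 1.96. Then P(|t₄| > 1.96) = 12.2% and P(|t₅| > 1.96) = 10.7%. The wrong reference alone more than doubles a 5% rate, before any bias in the sandwich variance.

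**Simulated rejection rates, no OARS effect.**

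| Analysis | Model A | Model B |
|---|---|---|
| Clinic-level sandwich, uncorrected, normal reference | 12-19%, including at ρ = 0 | 14-15% no time term; 15-22% linear; 18-24% categorical |
| Random clinic intercept, residual df | about 5% at ρ = 0; at ρ 0.5-0.9, 13-21% with a time term and 21-46% without | 5-6% at CAC 1.0; 9-16% at CAC 0.8 or 0.5 |
| Clinic ignored | not run | 7-18% no time term; 26-44% with one |
| AR(1) model, residual df | 4-8% | not run |
| ANOVA on clinic-period means, clinic fixed | 2-5% with a period term; 12-14% without, at ρ 0.8-0.9 | 4.3-5.5% |
| Paired t test on six clinics, no calendar trend | 4-6% | 4.6-5.7% |
| Bias-corrected sandwich (Kauermann-Carroll or CR2), t on 4 df | 3-5% | 3.5-6.7% |

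Changing only the reference is not enough: in Model B the uncorrected sandwich with t on 5 df still rejected up to 14.1% of the time (ICC 0.10, CAC 0.8, categorical periods).

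**Why the paired contrast needs a condition.** Every clinic's OARS months follow its usual-treatment months. For a clinic with m usual-treatment months, the mid-points of the two phases lie (m + 4.5) − (m + 1)/2 = (m + 8)/2 months apart: 6, 8 and 10 months for m = 4, 8 and 12, on average 8. An assumed calendar trend of 0.05 or 0.10 within-clinic SD per month then shifts a contrast of phase means by 8×0.05 = 0.4 or 8×0.10 = 0.8 SD with no OARS effect. At ρ = 0.8 the paired test rejected 13-16% and 43-44% of the time respectively.

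**The case against.** A reader might infer that the plan prescribes an invalid test, or that its primary tests have a false-positive rate of 12-20%. The documents do not support that. Section 6.3 names no SAS procedure and no level; the 5% used here is an assumption. An AR(1) model, a period-adjusted analysis of clinic-period means and a paired clinic contrast are all repeated-measures analyses, and each stays near 5% under its own conditions. Nor is the exchangeable model always invalid: it holds its level when there is no clinic-by-time correlation.

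The stated index-visit versus 6-month contrast also matters. If it means one value before and one after per clinic, exchangeable and decaying correlation are the same model, and a paired test holds 4-6% without a calendar trend.

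Finally, the documents give no autocorrelation, and the stock argument is strongest for caseload; it does not carry over directly to visits kept or urine results.

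All of this stands, and it makes the inflation conditional. It does not close the gap. The sandwich result needs no autocorrelation, only six clusters. The paired contrast is safe only without a trend, and section 1.1 describes a changing epidemic. Section 6.3 does not say whether its contrast is formed by clinic or by patient. Wording that admits tests with error rates from about 5% to over 40% leaves the error rate uncontrolled and the choice open until the data are seen.

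**Conclusion.** The concern holds as a conditional one: the plan does not secure valid inference for six clinics. At an assumed two-sided 5% level, the uncorrected clinic-level sandwich z test rejects a true null about 12-24% of the time whatever the autocorrelation. The exchangeable model rejects about 13-21% with a time term and 21-46% without, given assumed monthly autocorrelation of 0.5-0.9. Ignoring clinic can exceed 40% (Model B, ICC 0.10, CAC 0.8, time in the model). A bias-corrected sandwich with t on 4 df gave 3-7% in the settings run.

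The exact figures rest on normal outcomes and, in Model B, equal cell sizes. Counts, binary urine results, unequal clinics and patients contributing repeatedly would move them. The number of independent clusters would still be six.

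**What to change.** State in section 6.3, before outcome data are examined:

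- each primary outcome is analysed with clinic as the cluster and a calendar-time term in the model;
- inference uses a bias-corrected (Kauermann-Carroll or CR2) clinic-level sandwich variance with a t reference on about 4 df;
- uncorrected sandwich z tests, exchangeable errors with default df, and models that ignore clinic are not used for primary inference;
- the significance level and sidedness;
- how the index-visit versus 6-month contrast is formed (by clinic or by patient, and from which months) and how it fits this model.

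An AR(1) or other decaying covariance could be a sensitivity analysis; a Kenward-Roger version was not simulated here and should be checked on this layout first.

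The cost is SAP wording and a few program lines, with no new clinics, patients or data. Intervals widen: the change of reference alone multiplies their length by 2.776/1.960 = 1.42, and the variance correction adds to that.

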2.2 Secondary Objective

The secondary aim of this study is to assess the effect of provider and patient engagement with the OARS platform (number of days of OARS engagement, number of interactive features used) on patient opioid abstinence (opioid-negative urine toxicology).

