4.2 Inclusion Criteria

The research conducted in this study involves a review of patient medical records. In each clinic, the research team will work with clinic administrators to identify PCPs and patients treated by the PCPs using MAT who will contribute data to baseline and who will use the OARS platform when it is integrated into the EHRs at the determined date.

Clinics will need to meet the following criteria to participate in the study:

- Provide treatment to patients in the setting of primary care (e.g. family medicine, internal medicine)
- Have at least one provider with a DATA-2000 waiver who provides primary care and MAT to patients
- Have at least 35 patients receiving MAT for OUD
- Have an established EHR

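### The secondary logistic regression makes no allowance for clustering by provider or clinic, so its interval and p-value for provider engagement are likely to be too optimistic

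*Combined protocol and SAP*

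**What the plan says.** The secondary objective (2.2) is the effect of provider and patient engagement with OARS, measured by days of use and number of interactive features used, on patient abstinence. Section 6.3 gives the method in one sentence, "A logistic regression model will be employed to estimate effect of provider and patient engagement with the OARS platform", and then lists the adjustment set: "We will adjust for patient-level covariates including demographic variables", followed by other substance use, severity and comorbidity. No random effect, GEE, robust variance, or provider or clinic term is named for this model. Repeated-measures methods and clinic-level factors appear in 6.3 only for the primary analysis.

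On the outcome, Section 3.2 says that abstinence "will be assessed on a patient level as patients are treated for OUD under the OARS condition". On the exposure, Section 5 says that patient-level data from the OARS period will show how far "different levels of provider and patient engagement with OARS relate to opioid abstinence among patients". No section says whether provider engagement is one value per provider or a value recorded for each patient.

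On numbers, Section 4.1 states "The study population will consist of six primary care clinics" and says that across them "there is a minimum of 200 patients needed to provide statistical power to assess primary and secondary objectives". The inclusion list in 4.2 requires at least 35 MAT patients per clinic and, on providers, only this: "Have at least one provider with a DATA-2000 waiver who provides primary care and MAT to patients".

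**The concern.** How often a provider uses the platform, and how many features that provider uses, is most naturally a property of the provider. Every patient on the panel then carries the same, or nearly the same, value. Patients of one provider also tend to resemble one another in outcome, through case mix, prescribing style and urine-testing practice. When exposure and outcome both cluster, a model that treats patients as independent overstates the information about the exposure. Precision for provider engagement is limited by the number of providers, which the plan allows to be as low as six, and not by the 200 or more patients.

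At stake is the provider half of the secondary objective. A chance difference between a few providers' panels could be reported as evidence that provider use of OARS drives abstinence.

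**Working it through.** **Plan's own figure.** The 200-patient minimum cannot be reproduced, because no alpha, power, effect size, abstinence rate or ICC is given. The eligibility floor alone gives 6 × 35 = 210.

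**Inputs from the documents.** Six clinics and a 200-patient minimum (4.1); at least 35 patients and at least one waivered provider per clinic (4.2).

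**Assumed, because not given.** Two-sided alpha 0.05; outcome ICC by provider (ρy) 0.02 to 0.10; 6, 12 or 24 providers; 60% or 70% abstinent; no true effect; one outcome per patient.

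**Formula.** With m patients per provider and exposure ICC ρx (1 if fully shared within provider):

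- DEFF = 1 + (m − 1) × ρx × ρy
- actual error rate = 2 × [1 − Φ(1.96/√DEFF)]

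Worked example, one provider per clinic: m = 35, ρx = 1, ρy = 0.05. DEFF = 1 + 34 × 0.05 = 2.70 and √2.70 = 1.64. The naive standard error is 1/1.64 = 0.61 of the true one. The error rate is 2 × [1 − Φ(1.96/1.64)] = 23.3%. For this term the 210 patients carry the information of about 210/2.70 = 78.

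| Fully shared exposure (formula) | ICC 0.02 | ICC 0.05 | ICC 0.10 |
|---|---|---|---|
| 6 providers, m = 35 | 13.0% | 23.3% | 35.0% |
| 12 providers, m = 200/12 = 16.7 | 8.7% | 14.2% | 22.1% |
| 24 providers, m = 200/24 = 8.3 | 6.7% | 9.4% | 13.7% |

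**Simulation of the plain logistic fit.** 3,000 null runs per setting, provider random intercept, ICC on the logit scale, 60% abstinent:

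| Providers × patients | ICC 0 | ICC 0.02 | ICC 0.05 | ICC 0.10 |
|---|---|---|---|---|
| 6 × 35 | 5.1% | 10.9% | 21.5% | 30.6% |
| 12 × 17 | 5.2% | 7.4% | 11.9% | 19.1% |
| 20 × 10 | 5.4% | 6.2% | 9.1% | 13.0% |

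The scale of the ICC matters. At 6 × 35, ICC 0.05 and 70% abstinent, a simulation gave 17.9% on the logit scale and 22.6% on the proportion scale. Across both scales at 70% abstinent, ICC 0.02 to 0.10 gave 10–36% for 6 × 35, 7–24% for 12 × 17 and 7–13% for 24 × 9.

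**Provider engagement recorded per patient.** With ρx = 0.25, m = 35 and ρy = 0.10, DEFF = 1 + 34 × 0.25 × 0.10 = 1.85 and the error rate is 15.0%. With m = 17.5 and ρy = 0.02, DEFF = 1 + 16.5 × 0.25 × 0.02 = 1.08 and it is 6.0%. Over ρy 0.02 to 0.10 the range is 6.0–9.9% at m = 17.5 and 7.0–15.0% at m = 35.

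**Patient engagement.** For a term that varies independently within provider, ρx = 0, DEFF = 1 and the error rate stays at 5%. In the fully shared runs it was 4.1–5.4%.

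**Provider as the unit.** Correlating provider abstinence proportions with provider engagement, on (providers − 2) degrees of freedom, gave 4.4–5.7% in every setting simulated.

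**The case against.** The strongest reply is that the documents never say provider engagement is one value per provider. Section 5 calls the data patient-level, and Section 1.1 describes OARS as a place where patients interact with their providers, so engagement logged separately for each patient is an open reading. That stands. It reduces the inflation without removing it, and the missing definition is itself a gap in 6.3.

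Three stronger readings are tempting, and the documents do not support them.

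- A reader might infer a settled false-positive rate, for instance 17% or 26%. From DEFF = (1.96/z)², where z is the two-sided normal critical value for that rate, these need DEFF of about 2.04 and 3.03. That means an ICC of about 0.03 and 0.06 at 35 patients per provider, or about 0.066 and 0.13 at 16.7. None of these inputs is documented.
- A reader might infer that there will be only six to twelve providers. Section 4.2 sets a floor, and the limit of two PCPs per clinic in Section 5 applies to interviews. More prescribers are possible, and the problem shrinks as their number rises.
- A reader might infer that repeated urine tests will be pooled as independent rows, which would invalidate the patient-engagement result too. Sections 3.2 and 6.3 speak of abstinence at patient level, which favours one outcome per patient, although the row unit is not stated outright.

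It is also fair to say that this is a secondary, non-randomised association and that the primary comparison of OARS with TAU is untouched by this point.

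**Conclusion.** The concern holds for the provider-engagement term. As written, 6.3 treats patients as independent, and any positive ICC combined with an exposure that is wholly or partly shared within provider makes that term's standard error too small. The direction is firm; the size is conditional. At nominal two-sided 5%, outcome ICC 0.02 to 0.10 and a fully shared exposure, the false-positive rate is about 10–36% with six providers of 35 patients, 7–24% with 12 providers and 7–13% with 24. It is about 6–15% if engagement is recorded per patient with exposure ICC 0.25 and 17.5 to 35 patients per provider. Alpha, ICCs, abstinence rate and provider numbers are all assumptions. The patient-engagement term is not materially affected if it varies independently within provider and each patient contributes one outcome; it would be affected if it also clustered by provider or clinic.

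**What to change.** In Section 6.3:

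1. Define the level at which provider engagement is measured (provider or patient) and what one row of the analysis is.
2. Replace the plain logistic model with one that accounts for provider and clinic clustering and is corrected for few clusters. Either test provider engagement with the provider as the unit, or fit a logistic mixed model with a provider random intercept and clinic accounted for. Use a t reference with degrees of freedom based on the number of providers, or of clinics if each has one provider and the two levels coincide.
3. Add a patient random intercept only if repeated urine tests are the rows.
4. State that the 200-patient minimum in 4.1 does not set the precision of the provider-engagement result, and that this result will be reported descriptively if providers are too few.

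The cost is plan wording, provider and clinic identifiers in the analysis file, and a wider interval for provider engagement. With six providers, a provider-level test has only 6 − 2 = 4 degrees of freedom. No further data are needed from patients.
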